6 ANALYSIS SETS

Membership of the analysis sets will be reviewed and agreed at a Data Review Meeting (DRM) before database lock.

6.1 FULL ANALYSIS SET

The Full Analysis Set (FAS population) is defined as all patients included in the study, who have received at least one dose of the study treatment, and who have at least one baseline data.

The FAS will be used for examining demographics and other baseline characteristics. Number of doses will be presented on the FAS population.

6.2 SAFETY SET

The Safety dataset (SAF population) is defined as those patients included in the study, who have received at least one dose of the study treatment.

The Safety Set will be used for all safety analyses.

6.3 EFFICACY SET

6.3.1 “raw” Efficacy Set (Efficacy Set 1)

A “raw” efficacy set will take into consideration only patients at time point (N = nb of patients for whom efficacy variables are available at W12).

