8.2. Efficacy Analysis

Analysis of efficacy data will be carried out in the Full Analysis Set in which subjects who prematurely terminate the study will be considered failures.

The primary efficacy endpoint of the study, the ACR20 response rate, will be compared in subjects who received a given dose of ABX464 or placebo by likelihood ratio chi-square test on a 10% two-sided level.

The result of the test will be interpreted in a descriptive manner therefore no adjustment for multiple comparison is applied.

In addition, descriptive statistics will be presented by treatment arm for all secondary efficacy variables for each measurement timepoints separately for the two study groups.

These statistics include:

- Continuous variables: mean, standard deviation, minimum and maximum, stratified 95% confidence intervals, median and quartiles will be presented.
- Categorical variables: counts, rates and stratified 95% confidence intervals for the rates will be calculated.

In addition to descriptive statistics, mixed model analysis of covariance will be conducted for the following measurements:

- The change from baseline in DAS28-CRP and DAS28-ESR
- The change from baseline in the individual components of the ACR20 response (CRP, TJC(28), SJC(28), Pain-VAS, PtGA, PrGA, HAQ-DI) and in ESR
- The change from baseline in SDAI and CDAI scores
- The change from baseline in miR-124 in total blood at Week 8

In this model, treatments and stratum will be fixed effects, subjects will be random effect, and baseline values of the respective measurements will be covariates. Other explanatory variables will also be allowed to be included in the model. In order to normalize eventual skewed distributions transformation of the data will also be considered. Study groups will be compared within this model framework. All p-values will be interpreted in a descriptive manner.

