1.2 CHANGES FROM PROTOCOL

It is stated in the protocol that *“Analysis of efficacy data will be carried out in the Full Analysis Set in which subjects who prematurely terminate the study will be considered failures.”*

Sponsor requested by email having 2 efficacy set.

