6.3.2 Efficacy Set with imputation (Efficacy Set 2)

Another efficacy set will use data imputation (LOCF) from Week 4.

If there are no efficacy data available, then the dropout would be considered as treatment failure.

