11.3 EFFICACY ANALYSES

Analysis of efficacy data will be carried out on Efficacy Set 1 and will be repeated for Efficacy Set 2. Treatment comparisons will be ABX464 in two different doses vs. placebo.

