11.3.2 Secondary Variables

Descriptive statistics will be presented by treatment arm for all secondary efficacy variables for each measurement timepoints separately for the study groups:

- Proportion of patients achieving a categorical ACR20 response at Week 12 (Table 14.2.2.1 and Table 14.2.2.2).
- Change from Baseline in the individual components of the ACR20 response at Week 2, Week 4, Week 8 and Week 12 (Table 14.2.3.1 and Table 14.2.3.2):
 - C-Reactive Protein (CRP) (mg/L),
 - Tender/painful joint count (TJC) (28 joints),
 - Swollen joint count (SJC) (28 joints),
 - Patient assessment of joint pain (Pain-VAS),
 - Patient global assessment of disease (PtGA),
 - Physician's Global Assessment of Disease (PrGA),
 - HAQ-DI.
- Change from Baseline in the following disease parameters at Week 2, Week 4, Week 8 and Week 12:
 - ESR (Table 14.2.4.1.1 and Table 14.2.4.1.2);
 - DAS28-CRP (Table 14.2.4.2.1 and Table 14.2.4.2.2) and DAS28-ESR (Table 14.2.4.3.1 and Table 14.2.4.3.2);
 - SDAI score (Table 14.2.4.4.1 and Table 14.2.4.4.2);
 - CDAI score (Table 14.2.4.5.1 and Table 14.2.4.5.2);
 - FACIT-Fatigue score (Table 14.2.4.6.1 and Table 14.2.4.6.2).
- Proportion of patients achieving:
 - ACR20/50/70 response;
 - Categorical DAS28-CRP response;
 - LDA;
 - DAS28-ESR remission;
 - ACR/EULAR remission;
 - SDAI remission;
 - CDAI remission
 at Week 2, Week 4, Week 8 and Week 12 (Table 14.2.5.1 and Table 14.2.5.2).

These statistics include:

- Continuous variables: mean, standard deviation, minimum and maximum, stratified 95% confidence intervals, median and quartiles will be presented.
- Categorical variables: counts, rates and stratified 95% confidence intervals for the rates will be calculated.

In addition to descriptive statistics, mixed model analysis of covariance will be conducted for the following measurements:

- The change from baseline in DAS28-CRP and DAS28-ESR;
- The change from baseline in the individual components of the ACR20 response (CRP, TJC(28), SJC(28), Pain-VAS, PtGA, PrGA, HAQ-DI) and in ESR;
- The change from baseline in SDAI and CDAI scores.

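### No SAP table gives or tests the ACR20 comparison that the protocol plans (FAS, early terminators as failures), and SAP 6.3 conflicts with SAP 3.5 and 10.4

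*SAP*

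**What the plan says.** Protocol 8.2 states: "Analysis of efficacy data will be carried out in the Full Analysis Set in which subjects who prematurely terminate the study will be considered failures". ACR20 is then compared, each dose against placebo, by a likelihood ratio chi-square test at the 10% two-sided level.

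SAP 1.2 cites that sentence as changed and gives this explanation: "Sponsor requested by email having 2 efficacy set". The replacements are in SAP 6.3:

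- **Efficacy Set 1 (6.3.1).** The "efficacy set will take into consideration only patients at time point (N = nb of patients for whom efficacy variables are available at W12").
- **Efficacy Set 2 (6.3.2).** "Another efficacy set will use data imputation (LOCF) from Week 4". For patients with nothing to carry forward, the section adds this rule: "If there are no efficacy data available, then the dropout would be considered as treatment failure".

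SAP 11.3 then says: "Analysis of efficacy data will be carried out on Efficacy Set 1 and will be repeated for Efficacy Set 2". The ACR20 tables follow: 14.2.1.1 and 14.2.1.2 (tests on Sets 1 and 2), 14.2.1.3 (test on the PP Set), 14.2.2.1–2 and 14.2.5.1–2 (summaries on Sets 1 and 2, the latter "at Week 2, Week 4, Week 8 and Week 12 (Table 14.2.5.1 and Table 14.2.5.2"). On the FAS, SAP 6.1 says: "The FAS will be used for examining demographics and other baseline characteristics"; it adds only the number of doses. The FAS tables listed in SAP 14.1 cover demographics, medical history, exposure and compliance, and medications.

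Two other SAP sections bear on this. Section 3.5 repeats the protocol's planning argument that no dropout adjustment is needed because terminators count as failures. Section 10.4 permits proration of missing scale items and rules out any other imputation.

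**The concern.** Neither set reproduces the planned analysis.

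Set 1 selects patients on a post-randomisation event. Under protocol 5.2.5 an early stopper has an End of Study visit with no joint counts, VAS scores or HAQ-DI, so ACR20 cannot be derived from it and the patient leaves the denominator. Set 2 can do the opposite of the protocol rule: a patient who responds at Week 4 or Week 8 and then stops remains a responder. Its starting point is also unclear for a patient with Week 2 data only, although failure is a possible reading.

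ACR20 at Week 12 is the main efficacy endpoint and the basis of the sample size. With several p-values for it and none designated as main, the reported rate and p-value depend on which set is quoted. The SAP also cannot be followed as written: 6.3.2 imputes where 10.4 forbids it, and 3.5 relies on a rule that 6.3 has dropped.

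**Working it through.** **1. The plan's own figure.** Inputs from SAP 3.5 and protocol 8.6: 20 per arm, 0.65 v 0.25, 10% two-sided (z = 1.645). With pooled rate 0.45:

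- SE under the null: √(2 × 0.45 × 0.55 / 20) = 0.1573
- SE under the alternative: √(0.65 × 0.35 / 20 + 0.25 × 0.75 / 20) = 0.1440
- Power: Φ[(0.40 − 1.645 × 0.1573) / 0.1440] = Φ(0.980) = 83.7%

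Exact enumeration of the likelihood ratio test gives 83.3%. The stated 84% therefore reproduces when 0.65 and 0.25 are read as failure-rule rates. No loss of power is claimed.

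**2. The same patients under each rule.** The counts are assumed, because the documents give no dropout rate: 20 per arm; 4 active and 2 placebo patients stop early; 9 active and 5 placebo completers respond. The statistic is G² = 2 Σ O ln(O/E) on 1 df, with 10% critical value 2.706. For the protocol rule, the expected counts are 7 responders and 13 non-responders per arm:

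G² = 2[9 ln(9/7) + 11 ln(11/13) + 5 ln(5/7) + 15 ln(15/13)] = 1.777

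| Rule | Active | Placebo | G² | p |
|---|---|---|---|---|
| Protocol 8.2 | 9/20 (45%) | 5/20 (25%) | 1.777 | 0.18 |
| Set 1 | 9/16 (56%) | 5/18 (28%) | 2.869 | 0.090 |
| Set 2, no dropout carries a response | 9/20 | 5/20 | 1.777 | 0.18 |
| Set 2, one active dropout does | 10/20 | 5/20 | 2.7058 | 0.09999 |
| Set 2, one in each arm does | 10/20 | 6/20 | 1.681 | 0.195 |

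**3. Chance of an active-better result at the 10% level.** Exact enumeration, 20 per arm, counting rejections in which the active rate is higher. Assumed: a failure-rule response of 30% in both arms. Under the protocol rule the chance is 5.8%.

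*Set 1.* Each patient is a responder (30%), a dropout (d) or another non-responder (70% − d); the test uses completers only.

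| Dropout, active v placebo | Set 1 |
|---|---|
| 10% v 10% | 5.4% |
| 20% v 20% | 5.5% |
| 10% v 5% | 6.7% |
| 15% v 10% | 6.9% |
| 20% v 10% | 8.9% |
| 25% v 5% | 13.7% |
| 10% v 20% | 3.3% |
| 5% v 25% | 1.9% |

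*Set 2.* The response probability is 30% + f × d, where f is the share of dropouts who carry a response forward.

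| Dropout, active v placebo | f = 0 | f = 15% | f = 30% | f = 50% |
|---|---|---|---|---|
| 15% v 10% | 5.8% | 6.5% | 7.1% | 7.9% |
| 20% v 10% | 5.8% | 7.1% | 8.6% | 10.4% |
| 25% v 5% | 5.8% | 8.6% | 12.1% | 17.5% |

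**4. What these percentages measure.** They are judged against the protocol's failure-rule response. Under that null the completers truly differ, because the completer rate is 0.30 / (1 − d): 0.30/0.80 = 37.5% v 0.30/0.90 = 33.3% at 20% v 10% dropout, and 0.30/0.75 = 40.0% v 0.30/0.95 = 31.6% at 25% v 5%. Set 1 thus estimates a different quantity.

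**The case against.** The strongest reply is that the change is declared, the endpoint is secondary, and little information is lost. SAP 1.2 lists the departure. The primary objective is safety, analysed on the Safety Set, and the ACR20 p-values are descriptive and unadjusted. A reader can normally recover the failure-rule rate by dividing the responder count in Table 14.2.1.1 by the FAS N in Table 14.1.2, and could then redo the test. SAP 11.3 also puts Set 1 first, which suggests that it leads.

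The size rests on assumed dropout, and the example is sensitive to the split. Keeping 9 and 5 responders, Set 1 gives p = 0.127 with 3 v 2 stoppers (9/17 v 5/18), 0.152 with 4 v 4 (9/16 v 5/16) and 0.169 with 2 v 2 (9/18 v 5/18). None crosses 10%. The 25% v 5% case needs a 20-point imbalance.

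Most of this stands as a limit on weight: the effect may be small, absent or reversed. It does not remove the mismatch. A declared change still needs a reason and a designated main analysis, and being listed first is not a designation. A comparison that readers must rebuild for themselves is neither tabulated nor tested. The general wording of 10.4 may well yield to the specific rule in 6.3.2 in practice, but the text says otherwise. It is also fair to say that protocol 8.2 applies its failure rule to efficacy data generally, whereas this point covers ACR20 only.

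**Conclusion.** The concern holds. The planned ACR20 comparison appears in no SAP table, neither substitute set is equivalent to it, and SAP 6.3 is inconsistent with 3.5 (failure rule) and, through 6.3.2, with 10.4 (imputation).

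The consequence is moderate. For Set 1, the chance of an active-better result at equal failure-rule response stays near 5.8% with equal dropout, rises to 6.7–8.9% with a 5- to 10-point excess of active dropout and to 13.7% with a 20-point excess, and falls below 5.8% when placebo loses more patients. For Set 2 it depends also on how many dropouts carry a response forward. All of this assumes 20 per arm, a 30% response, and the stated dropout rates and carry-forward shares; the documents supply none of the last three. The defect should be corrected before database lock, but it does not touch the primary safety analysis.

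**What to change.** Before database lock, amend SAP 6.1, 6.3 and 11.3, Tables 14.2.1.x and 14.2.2.x, and the Week 12 ACR20 rows of 14.2.5.x:

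- Make the FAS with premature terminators as failures the main ACR20 analysis, as protocol 8.2 plans. State that the denominator is the FAS N, because SAP 10.1 otherwise defaults to non-missing observations.
- Keep Efficacy Sets 1 and 2 as labelled sensitivity analyses.
- State in 6.3.2 what carrying forward from Week 4 means for a patient with Week 2 data only.
- Reconcile SAP 3.5 and 10.4 with 6.3.
- For this rule, define premature termination by whether the 12-week treatment period was completed. Do not use the completed status of Table 14.1.3: its footnote ties that status to the follow-up visit, which protocol 5.2.5 gives to early stoppers but not to patients entering the maintenance study.
- Optional, beyond protocol 8.2: count completers with a missing Week 12 ACR20 as non-responders.

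The blind data review meeting in SAP 9.4 is a suitable place to settle this. The cost is SAP wording and one more run of existing shells. Reported rates may be lower than in Set 1, by an amount that depends on dropout; in the example, 56% becomes 45% on active and 28% becomes 25% on placebo.

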5.2.5. End of Study Visit (Week 15 / Day 105 ± 2 days)

This EOS visit applies to all premature discontinued patients and to patients not taking part to the maintenance study. Patients will perform an End of Study Visit (EOS) three weeks after last dosing. Patients will be treated according to the standard of care since the last day of study treatment.

Following examinations/procedures should be performed:

- Physical examination and vital signs;
- Body weight;
- Hematology and Biochemistry panel;
- Blood pregnancy test for all women of childbearing potential;
- Pharmacokinetics blood samples trough levels;
- 12 leads ECG (in case of premature discontinuation only);
- Record any concomitant medications;
- Adverse Events reporting.

NB#1: In case of premature discontinuation occurring during the treatment phase (D1-D84), the above examinations should be performed as an End of Study Visit.

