8.1.1. Protocol deviations

Protocol deviations will be reviewed and classed as major or minor during the blind-review meeting. Major protocol deviations are defined as deviations liable to bias the evaluation of the main efficacy endpoint. The following deviations will be considered as major (non-exhaustive list):

- Noncompliance with the inclusion or exclusion criteria;
- Noncompliance with the study treatment;
- Intake of prohibited medication;
- Noncompliance with time window.

In case of major protocol deviation, the patient must not be randomized (if deviation occurs at baseline) or be discontinued from the study.

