5.2.10 Categorical ACR20/50/70 response

The component of ACR assessment include:

- tender/painful joint count (28),
- swollen joint count (28),
- patient assessment of joint pain,
- Patient Global Assessment of Disease (PtGA)
- Physician's Global Assessment of Disease (PrGA),

- CRP and
- Disability index of the healthy assessment questionnaire (HAQ-DI).

Patient assessment of joint pain: VAS scale 0-10 cm.

PtGA: Patient Global Assessment of disease activity (VAS scale 0 – 10cm).

PrGA: Physician Global Assessment of disease activity (VAS scale 0 – 10cm).

HAQ-DI: This patient reported outcome questionnaire is usually self-administered by the patient.

The following 8 categories are assessed by the HAQ-DI:

1. Dressing and grooming
2. Arising
3. Eating
4. Walking
5. Hygiene
6. Reach
7. Grip
8. Common daily activities

The patients report the amount of difficulty they have in performing some of these activities. Each question asks on a scale ranging from 0 to 3 if the categories can be performed without any difficulty (scale 0) up to cannot be done at all (scale 3).

The highest score reported by the patient for any component question of the eight categories determines the score for that category. The sum of the computed categories scores is calculated and divided by the number of categories answered. This gives a total score in the 0 to 3 range.

Definition of the ACR20% response:

- $\geq 20\%$ improvement in tender joint counts
- $\geq 20\%$ improvement swollen joint counts
- $\geq 20\%$ improvement in 3 of the 5 remaining ACR core set measures:
 - PtGA,
 - PrGA,
 - patient assessment of joint pain,
 - HAQ-DI,

- CRP.

For ACR50% and ACR70%, an improvement of respectively 50 and 70% of the same parameters has to be observed.

5.2.11 Functional Assessment of Chronic Illness Therapy (FACIT)-Fatigue:

This questionnaire is a measure to assess the patient fatigue in chronic diseases, and is validated in RA. It includes 13 items.

The FACIT score calculation process is defined as follows:

FACIT-Fatigue Subscale Scoring Guidelines (Version 4) – Page 1

- Instructions:*
1. Record answers in "item response" column. If missing, mark with an X
 2. Perform reversals as indicated, and sum individual items to obtain a score.
 3. Multiply the sum of the item scores by the number of items in the subscale, then divide by the number of items answered. This produces the subscale score.
 4. **The higher the score, the better the QOL.**

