10.4 MISSING DATA

For total scores and subscales with missing items the following rule will be used:

If < 50% of the scale items are missing, the total (or subscale total) will be calculated using the mean score of the non-missing items for that scale or subscale to impute a score for the missing items. In practice the score is derived using the formula:

$$\text{total of non-missing items} \times \text{number of items in (sub)scale} / \text{number of non-missing items}$$

If > 50% of the items were missing, no scale or subscale score will be calculated; the score will be considered missing.

There will be no other imputation of missing data in this study.

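### ACR20 is scored with no rule for patients who start or increase RA medication before Week 12, so a response produced by added drug can count as a treatment response

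*SAP*

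**What the plan says.** SAP 5.2.10 defines ACR20 as at least 20% improvement in tender and swollen joint counts plus "improvement in 3 of the 5 remaining ACR core set measures". It sets no medication condition; ACR50 and ACR70 follow the same pattern.

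Protocol 8.2 analyses efficacy in the Full Analysis Set, where "subjects who prematurely terminate the study will be considered failures". SAP 1.2 cites that rule as changed and gives one line of explanation: "Sponsor requested by email having 2 efficacy set". The two sets are in SAP 6.3:

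- Set 1 "will take into consideration only patients at time point (N = nb of patients for whom efficacy variables are available at W12".
- For Set 2: "Another efficacy set will use data imputation (LOCF) from Week 4". A dropout is a failure only if there are no efficacy data.

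SAP 10.4, after a rule for missing questionnaire items, adds: "There will be no other imputation of missing data in this study". SAP 11.3 runs the ACR20 test on Set 1 and repeats it on Set 2; Table 14.2.1.3 adds the per-protocol set.

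On conduct, Protocol 5.12.1 and 5.12.2 require stable MTX, corticosteroid, NSAID and analgesic doses. Section 5.12.3 lists prohibited drugs. Section 8.1.1 makes prohibited medication a major deviation and says: "In case of major protocol deviation, the patient must not be randomized (if deviation occurs at baseline) or be discontinued from the study".

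**The concern.** A patient doing badly on study drug may be given more steroid, a higher MTX dose or another DMARD. If the joint counts then improve, the improvement belongs at least partly to the added drug. Followed literally, the SAP can record this patient as an ACR20 responder for the randomised arm.

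Under the protocol, prohibited medication leads to discontinuation (8.1.1), and an early terminator is a failure (8.2). The SAP removes the second step and puts no medication rule in its place.

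At stake is the reading of the main efficacy endpoint, on which the sample size is based, in a study that Protocol 1.3 describes as proof of concept. With arms of about 20, a few misclassified patients are visible in the response rates.

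**Working it through.** **1. Which patients are affected.**

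- *Route (a): medicated and stays to Week 12.* Week 12 data exist, so the patient is in Set 1 and nothing needs imputing in Set 2. Both sets use the medicated value.
- *Route (b): medicated, then discontinued after a later efficacy visit.* The patient is outside Set 1. In Set 2 the carried value can be post-medication. If the LOCF wording means that only the Week 4 value is carried, this is limited to medication started before Week 4.
- *Medicated and discontinued promptly.* Not affected. Of the end-of-study visit, Protocol 5.2.5 says "This EOS visit applies to all premature discontinued patients and to patients not taking part to the maintenance study", but that visit has no joint counts, VAS or HAQ-DI. The patient is outside Set 1 and normally carries a pre-medication value in Set 2.

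**2. Whether the conduct rules close routes (a) and (b).**

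- Protocol 8.1.1 classes deviations as major or minor at the blind-review meeting. SAP 9.4 places that meeting when the final data are considered clean, so a medicated Week 12 value may already exist.
- Neither Protocol 8.1.1 nor SAP 6.4 names MTX or steroid dose increases among the major deviations. Both lists are non-exhaustive.
- Protocol 5.12.3 names non-anti-TNFα biologics and targeted DMARDs. Anti-TNFα and csDMARD starts are not named. They are caught only if read as immunosuppressive drugs.
- The per-protocol set excludes patients judged to have a major deviation. It does not count them as failures.

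**3. The plan's own figure.** Inputs from SAP 3.5: rates 0.65 and 0.25, 20 per arm, two-sided 10% level.

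Power = Φ[(d − z·SE0)/SE1], with d = 0.40 and z = 1.645.

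SE0 = √(2 × 0.45 × 0.55/20) = 0.157

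SE1 = √[(0.65 × 0.35 + 0.25 × 0.75)/20] = 0.144

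This gives 0.837. Exact enumeration of the likelihood ratio test gives 0.833. The stated 84% is reproduced.

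**4. Effect of converted patients.** The number and arm of conversions are assumed. The test is G = 2 Σ O ln(O/E), 1 df, 20 v 20. The planned rates correspond to 13/20 and 5/20.

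| Assumed conversions | ABX464 v placebo | Difference (points) | G | p |
|---|---|---|---|---|
| None | 13 v 5 | 40 | 6.66 | 0.010 |
| 1 placebo | 13 v 6 | 35 | 5.02 | 0.025 |
| 2 placebo | 13 v 7 | 30 | 3.66 | 0.056 |
| 3 placebo | 13 v 8 | 25 | 2.53 | 0.11 |
| 3 placebo, 1 active | 14 v 8 | 30 | 3.70 | 0.055 |
| 1 in each arm | 14 v 6 | 40 | 6.58 | 0.010 |
| 1 active | 14 v 5 | 45 | 8.42 | 0.0037 |

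One conversion is 1/20 = 5 points. In a Set 1 arm of, say, 18 it is 1/18 = 5.6 points.

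**5. Effect on power, also assumed.** Suppose 5%, 10%, 15% or 20% of placebo patients are medicated, would otherwise be non-responders, and half respond on the added drug. The scored placebo rate becomes 0.275, 0.30, 0.325 or 0.35, and power falls to 0.79, 0.73, 0.67 or 0.60.

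**The case against.** The strongest defence is that the conduct rules handle most of this. The study lasts 12 weeks and has no rescue provision. Background doses must be stable, worsening RA is a listed reason for withdrawal (Protocol 6.2), and deviations go to a blind review before lock. For a prohibited drug, route (a) needs a breach followed by a failure to discontinue. This stands as a reason to expect few cases. It does not supply a scoring rule, and it is weakest for dose increases and for the drug starts that 5.12.3 does not name.

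Scoring observed outcomes whatever the medication is also a recognised choice for a raw set. But the SAP does not state that choice, and its second set does not offer the alternative. Nor does Protocol 8.2 reach medicated patients who stay on study: it fails early terminators. A scoring rule for those patients is consistent with the protocol's intent but goes beyond its text.

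A reader might infer that every medicated patient distorts the rate by 5 points. That is too strong: one who would have responded anyway, or who still fails, changes nothing. A reader might equally infer that new RA drugs are all barred and that the per-protocol table removes every affected patient. The text does not support that either, for the reasons in the second step of the working.

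**Conclusion.** The gap is real and should be closed before unblinding. Read literally, the SAP can count as a responder a patient whose steroid, MTX or DMARD was raised before Week 12, and the protocol's safeguards do not reliably prevent it.

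The size is about 5 points per converted patient. At the planned rates, three conversions on placebo with none on ABX464 would take the comparison past the 10% level; two would not. These counts are assumptions, because the documents give no rate of medication change. The number affected is probably small.

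A reader might infer a bias in a known direction, or a threat to the trial's main conclusion. The documents support neither. Conversions on placebo shrink the contrast, conversions on ABX464 inflate it, and one in each arm leaves it at 40 points. The primary endpoint is safety, and the ACR20 test is declared descriptive (SAP 11.3.1). What is affected is the proof-of-concept reading of the response rates.

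**What to change.** Add to SAP 5.2.10 and 6.3: a patient who starts or increases a biologic (including anti-TNFα), a targeted DMARD, a csDMARD (including MTX), or a systemic or intra-articular glucocorticoid before the Week 12 assessment is an ACR20/50/70 non-responder at every later visit.

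- In Set 1 the rule applies to patients with Week 12 data; membership is unchanged.
- In Set 2 it applies to all such patients, and post-medication values are not carried forward.

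Identify the cases blind, before lock, from Listings 16.4.12.2 and 16.4.12.3, using their dose and start-date columns. Table 14.3.9.2 is not enough, because SAP 11.8 defines a change as a medication started on or after Day 1.

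The cost is a short SAP addition and one blinded check of data already collected, with no protocol amendment. A few patients in any arm may move from responder to non-responder, and dose increases need a simple derivation. The rule leaves two matters open. Withdrawal for worsening RA without new medication is still handled by the two sets as written. NSAID and analgesic increases, which could affect the pain and global scores, are not covered unless the sponsor adds them.

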In this model, treatments and stratum will be fixed effects, subjects will be random effect, and baseline values of the respective measurements will be covariates. Other explanatory variables will also be allowed to be included in the model. In order to normalize eventual skewed distributions transformation of the data will also be considered. Study groups will be compared within this model framework. All p-values will be interpreted in a descriptive manner.

All other analyses will be descriptive.

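### The SAP fits the mixed models for the 12 change-from-baseline outcomes only to Efficacy Sets 1 and 2, so no planned model uses all observed, un-imputed data in the FAS

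*SAP*

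**What the plan says.** Protocol 8.2 puts the efficacy analysis, including the mixed model analysis of covariance, in the FAS. It describes no imputation of continuous values.

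SAP 11.3 replaces this: "Analysis of efficacy data will be carried out on Efficacy Set 1 and will be repeated for Efficacy Set 2". The only reason given, in SAP 1.2, is a sponsor request. The SAP keeps the FAS for other purposes ("The FAS will be used for examining demographics and other baseline characteristics"), together with doses, exposure and medications.

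- **Efficacy Set 1 (SAP 6.3.1)** "will take into consideration only patients at time point", with N described as "nb of patients for whom efficacy variables are available at W12".
- **Efficacy Set 2 (SAP 6.3.2):** "Another efficacy set will use data imputation (LOCF) from Week 4". It adds: "If there are no efficacy data available, then the dropout would be considered as treatment failure".
- **Missing data (SAP 10.4):** after a rule for missing questionnaire items, "There will be no other imputation of missing data in this study".
- **Model (SAP 11.3.2):** treatment and stratum are fixed effects, and "subjects will be random effect, and baseline values of the respective measurements will be covariates". No visit or treatment-by-visit term is named.

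The model covers 12 outcomes measured at Weeks 2, 4, 8 and 12: DAS28-CRP, DAS28-ESR, the seven ACR components, ESR, SDAI and CDAI (2 + 7 + 1 + 2). Their tables (14.2.3.x and 14.2.4.1.x to 14.2.4.5.x) exist only for Sets 1 and 2. The Per Protocol Set has one efficacy table, for ACR20. The FAS has none.

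**The concern.** A likelihood model with a random subject effect can use patients with incomplete follow-up without deleting or inventing values. The SAP specifies such a model but applies it only where that advantage is lost.

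If Set 1 means patients with Week 12 data, someone who leaves after Week 8 also disappears from the Week 2, 4 and 8 comparisons. Early dose effects are then conditioned on later staying in the trial. In Set 2 the carried-forward values enter the model as if they had been measured. The failure rule in Set 2 has no meaning for a change in CRP or DAS28, and 6.3.2 does not say what happens to a patient whose only post-baseline value is at Week 2.

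Missingness related to response is plausible here. Protocol 6.2 lists worsening of RA as a reason for discontinuation, and Protocol 8.1.1 calls for discontinuation after a major deviation. The End of Study visit in Protocol 5.2.5 includes no joint counts, VAS scores or HAQ-DI. For an early leaver, the scheduled visits before leaving are therefore the only source of post-baseline composite scores.

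**Working it through.** **1. The plan's own figure.** The documents give no design figure for the mixed models. The only efficacy figure is 84% power for ACR20 (Protocol 8.6): 20 per arm, 0.65 against 0.25, 10% two-sided. With a pooled rate of 0.45:

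- null SE = sqrt(2 × 0.45 × 0.55 / 20) = 0.1573
- alternative SE = sqrt((0.65 × 0.35 + 0.25 × 0.75) / 20) = 0.1441
- power = Φ((0.40 - 1.645 × 0.1573) / 0.1441) = Φ(0.98) = 0.837

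The figure reproduces and is not affected by this point.

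**2. Observations affected.** There are 60 patients and 4 post-baseline visits, so 240 cells. Assume k drop-outs, leaving in equal thirds after Weeks 2, 4 and 8.

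- Observed visits of drop-outs = (k/3)(1 + 2 + 3) = 2k. The Week 12 reading of Set 1 deletes all of these.
- Cells filled by full LOCF = (k/3)(3 + 2 + 1) = 2k.

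| Drop-out | k | Deleted by Set 1 | Share of all observed | Filled by LOCF, share of 240 |
|---|---|---|---|---|
| 5% | 3 | 6 | 6/234 = 2.6% | 2.5% |
| 10% | 6 | 12 | 12/228 = 5.3% | 5% |
| 20% | 12 | 24 | 24/216 = 11.1% | 10% |
| 30% | 18 | 36 | 36/204 = 17.6% | 15% |

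If Week 2 values are not carried forward, the filled cells fall to (k/3)(2 + 1) = k.

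**3. Week 12 bias, by simulation.** None of these inputs is in the documents.

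- SD of DAS28 change 1.2; between-visit correlation 0.6.
- Mean changes at Weeks 2, 4, 8 and 12: placebo -0.3, -0.5, -0.7, -0.8; active -0.5, -0.9, -1.3, -1.6. The true Week 12 difference is -0.80.
- Patients with a worse observed response are more likely to leave after Weeks 2, 4 and 8 (missing at random).
- 300 simulated trials of 500 per arm, to show bias.

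| Nominal drop-out, active / placebo | Completers | LOCF | Likelihood, all observed |
|---|---|---|---|
| 10% / 10% | -0.795 | -0.758 | -0.796 |
| 20% / 20% | -0.794 | -0.717 | -0.795 |
| 25% / 5% | -0.926 | -0.571 | -0.799 |
| 5% / 25% | -0.676 | -0.915 | -0.804 |

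With 20 per arm the means are similar, and the standard deviation of one trial's estimate is about 0.40. The completer shift of about 0.13 is then 0.13/0.40, or a third of that. The largest LOCF shift is 0.80 - 0.57 = 0.23, a little over half.

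**4. Early visits.** A separate simulation used the same SD, correlation and Week 12 difference, with drop-out only after Week 4 or 8 (27% placebo, 18% active). Nobody has left by Week 4. Even so, the completer-only placebo mean at Week 4 is -0.80 instead of -0.49, and the difference is -0.32 instead of -0.41. In a similar run (28% / 19%), LOCF gave -0.40 at Week 4 against a true -0.41.

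**5. Model terms.** A treatment effect without visit terms averages over visits. With complete data and the means in step 3 it is (-0.20 - 0.40 - 0.60 - 0.80)/4 = -0.50, not -0.80. With drop-out, in the 28% / 19% run, it was -0.47. Adding visit and treatment-by-visit terms gave -0.79 at Week 12.

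**The case against.** **Set 1 may not be a completer set.** The phrase "will take into consideration only patients at time point", with an N and a p-value at each visit in the shells for Tables 14.2.3.1 and 14.2.4.1.1, allows a by-visit available-case reading. In that case nothing observed is deleted. Against this, N is tied to Week 12, Table 14.1.2 gives one Set 1 count per arm, and Listing 16.2.3 gives one yes/no flag per patient. The completer reading is more natural but not certain. A reader might infer that the SAP definitely discards the early data. The text does not support that much.

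**Set 2 keeps observed early values.** LOCF leaves Week 2, 4 and 8 measurements at their own visits and adds later fills. The early-visit distortion in step 4 belongs to Set 1 alone, and every analysis is repeated on Set 2. This stands. The defect in Set 2 is that filled values are modelled as data.

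**Importance.** These are secondary endpoints in a safety-primary Phase IIa trial with descriptive p-values, the change of analysis set is declared, and the simulated shifts are below the sampling error of a single trial. This stands too, and it limits the severity.

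**Rerunning the planned program on the FAS may not help.** This is correct. As written, the model averages over visits. A by-visit analysis of covariance on the FAS would use the same Week 12 patients as Set 1. The visit terms must be part of the change.

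**FACIT-Fatigue.** A reader might count its absence from the model list as part of the same defect. Protocol 8.2 leaves it off as well, so it is a consistent choice unrelated to missing data.

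**Conclusion.** The point holds as a moderate one. No planned mixed model uses all observed, un-imputed FAS data, which departs from Protocol 8.2 without a statistical reason. SAP 6.3.2 contradicts 10.4, and its failure rule cannot be applied to a continuous change.

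A reader might infer that completer analysis always makes the treatment difference look smaller. The documents do not support a direction. In the simulation it was smaller when placebo lost more patients (-0.68) and larger when active did (-0.93), while LOCF moved the other way (-0.92 and -0.57). The two planned analyses can therefore disagree with nothing planned to arbitrate between them.

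The size depends on drop-out, which the documents do not give. At 5% drop-out about 2.6% of observed visits are affected, and with equal 10% drop-out the completer estimate hardly moves. The simulated figures also assume that drop-out depends only on observed response. Under other mechanisms the all-observed model can be biased too.

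**What to change.** - **SAP 11.3.2:** fit the mixed model to all observed Week 2, 4, 8 and 12 values in the FAS. Add visit and treatment-by-visit terms to treatment, stratum, baseline and subject. Report each dose-versus-placebo difference at each visit.
- **By-visit summaries:** base them on all FAS patients with data at that visit.
- **Efficacy Sets 1 and 2:** keep them as sensitivity analyses.
- **SAP 6.3.1:** state whether Set 1 is fixed by Week 12 data or defined visit by visit.
- **SAP 6.3.2 and 10.4:** reconcile them. State which values are carried forward, how a patient with only Week 2 data is handled, and that the failure rule applies to responder outcomes only.

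The cost is SAP wording, a modest program change and one added set of tables. No new data are needed, and sample size and significance levels do not change.
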